12) To answer the secondary research questions, starting in the second month after implementation, study manager will carry out **in-depth interviews** (or small focus group discussions) with providers at sites in both study groups. We will interview providers who use the paper partograph or the ePartogram to discuss barriers and facilitators to usage, including facility conditions. The supervision for providers around the ePartogram and paper-partograph use will also be explored. The interviews will be audio-recorded to capture all contributions from participants. Participants will be informed about this during consenting. The digital recorders erased/audio tapes will be destroyed after transcription and the recordings will not be used for any other purposes.

B. Provide a **sample size and a justification** as to how you arrived at that number. If you use screening procedures to arrive at a final sample a table may be helpful.

The third study objective deals with clinical actions for complications and requires the largest sample size due to the rarity of complications. We describe inputs to sample size as shown in Table 1.

Inputs to the sample size calculation are as follows:

- *Number of sites*: The available 12 sites (6 in each study arm) have 1342 births per month, , on average. So 6 facilities have 671 births per month. We believe 80% of these will have a partograph completed during the study.
- *Prevalence*: Kenya QoC report⁹ stated that “19% of labors crossed the partograph ‘action line’”. While this appears high, we also will look for labors with more than one abnormal measurement signaling an early complication. (A study by Orji et al in Nigeria in 2008 also found 18.5% of labors crossed the action line.) For our study, we use the 19% to indicate that up to 19% of labor may cross the action line OR may have 1+ abnormal measurement that signal need for provider action.
- *Average cluster size*: is calculated to be 17.6
- *Intraclass correlation*: ICC is expected to be high as the facilities are a heterogeneous mix of district hospitals, health centers and some private facilities, so we assume ICC of 0.15.
- *Coefficient of variation*: COV is assumed to be 90%, after calculating the standard deviation of the average monthly births in these sites. Therefore, the design effect is high at 5.3, calculated as follows: $1 + ((\text{average cluster size } 16.4 - 1) * (1 + (\text{COV } 0.80^2)) * \text{ICC } 0.15)$.

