In the exercise of completing the Health Worker Line Listing at each facility, we will document the numbers of cadres (Kenya Enrolled Community Health Nurses; Kenya Registered Community Health Nurses; Kenya Registered Nurses; Kenya Registered Nurse Midwives and Bachelor of Science in Nursing Nurses) and doctors (ObGyn and medical officers). A purposive sample of all cadres using the ePartogram or partograph will be selected. At high-volume sites, a sample of half of the providers on duty in a month and half of the supervisors will be interviewed. At lower-volume sites: all providers and supervisors will be interviewed. We will also interview each facility in-charge and district authority. So there are 4 respondent types: providers, supervisors, facility-in-charge and district authority.

The study staff will carry out the interviews when visiting the facility starting in second month. Each facility will have qualitative data collected at one point in time.

For the qualitative data, we will select 8 busy facilities: assume 2 to 8 providers per site (average 4 providers), $8*4 = 32$. One supervisor from each site: 8. Up to 4 in-charges and 4 district authorities. **Total 48 participants**. Note these qualitative participants will be part of the larger group of participants who consent to be part of the in the overall study.

IV. Participants

Describe the study participants and the population from which they will be drawn. Specify the inclusion and exclusion criteria. If you plan to include children, note their ages and whether you will include children in foster care. Note if the participants are particularly vulnerable in terms of cognitive limitations, education, legal migration status, incarceration, poverty, or some combination of factors.

Facilities

The facilities will include the higher referral-level hospitals in Kisumu and Meru, as well as lower level hospitals. The facilities will include both BEmONC and CEmONC sites.

Facility Inclusion Criteria:

- In Kisumu or Meru
- BEmONC or CEmONC sites
- At least one SBA on duty in labor ward 24 hours per day
- Facility in-charge or in-charge of L&D ward available physically or remotely 24 hours per day
- Use WHO modified paper partograph
- Adequate supply of paper partographs and maternity registers
- Availability of reliable transportation for referrals (e.g. functional ambulance or other) 24 hours per day

Facility Exclusion Criteria:

- Facility not registered with MOH

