- No SBA on duty in labor ward at any time during a 24 hour period
- No in-charge available at any time during a 24 hour period
- Dispensary health facilities that do not practice BEmONC

Facility in-charges

Following MOH letter approval and County approval, we will seek approval from the facility in-charge and maternity in-charge. The in-charges may serve as qualitative interviewees.

Providers – for ePartograph and paper partograph data review

Providers will give individual written consent to the study and each can voluntarily decline or opt out. All providers in a selected facility will be consented to the same study arm (ePartogram or paper partograph). The intervention will start with the training on labor management, partograph (and for intervention group, the ePartogram tablet use). Providers may be invited to participate in qualitative interviews.

Inclusion:

- 1) Providers meeting the WHO definition of Skilled Birth Attendant (SBA)⁴ clinical provider working in care for laboring women who will be working at the facility during the study.
- 2) Providers completing the three-day labor management training comprised of training on partograph use and management of normal labors and labor complications, according to WHO and Kenya MOH guidelines
- 3) Intervention sites only: Providers passing the ePartogram post-training test will be asked to use the ePartogram during clinical care.

Exclusion:

- 1) Providers not meeting the WHO definition of SBA
- 2) Providers not completing the labor management training or (intervention sites only) not passing the ePartogram post-training test

We plan to obtain written consent from all providers prior to the training. Any provider that joins the study during the study period who is in the ePartogram group B would need to receive one-on-one orientation without study coordinator or onsite trained providers and pass the ePartogram post-training skills test, prior to being consented to join the study. We will enroll no more than 200 providers.

Providers who join the study at paper partograph sites, after the training, will be asked to consent when the study coordinator visits the sites.

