1	Health Worker Line Listing	Study team will use this to assign a unique provider id to skilled birth attendants working in each facility who consented to the study and were trained by study staff. This provider study id will then be written on paper partographs, in ePartograms and on registers, when names are obscured (to account for clustering of data in the provider). We will record cadre, years of experience, and date passed labor management and ePartogram competency test.
2	Partograph or ePartogram file on each laboring woman (a)	The top portion of the partogram is completed on admission with information about: woman's name, gravida, parity, hospital id number, date and time of admission, and whether membranes are ruptured. At regular intervals, the following measurements are obtained by the provider: fetal heart rate, condition of amniotic fluid, moulding, descent of head, cervical dilation, contractions, oxytocin, drugs and IV fluids given, pulse, blood pressure, temperature, urine protein, acetone and volume.
3	Stamp on the paper partograph or programmed into the app (for ePartogram).	In this study, the paper partograph and ePartogram will include additional fields related to maintaining normal labor and management of abnormal conditions. The stamp will be placed on the paper partograph or programmed into the app (for ePartogram). Standard provider actions will be recorded (e.g. ambulation, nutrition, fluid intake, presence of a birth companion, oxygen administration, changing the mother's position for choice or due to fetal heart rate, presence of bleeding). Providers will also indicate if a consultation with another provider was made for the client and if the client was transferred (reason for referral), fresh stillbirth, or early newborn death.

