
P1. Compliance with globally-recommended labor monitoring practices and recording on the partograph of the information obtained – complete on admission (Tool 4)
	
We will examine each parameter and enter to the database.
 
Overall, this will be marked ‘yes’ if 11 of the 12 items (all except urine volume) are measured at admission (fetal heart rate, cervical dilation, systolic and diastolic blood pressure, amniotic fluid, moulding, head descent, contractions, pulse, temperature, urine protein, acetone and volume); and otherwise ‘no’. Binary variable.
	
All labors with partograph or ePartogram
 
Unit of analysis is each case (partograph).
	
First, we will examine the frequency/prevalence of each measurement recorded on admission and compare between the two study groups
 
Second, We will examine the percent of cases marked ‘yes’ (defined at left). Independent variable is study group. Bivariate analysis will be an unadjusted logistic regression accounting for clustering in the facility or in the provider. In multivariable analysis, other control factors added may be facility type, client volume, region or provider variables.

- Complete over entire labor (Tool 4)
	
We will examine each parameter and enter to the database. Then we will see how many hours was the labor for the appropriate frequency, per the Jhpiego Clinical Rules and determine whether this was done to a large extent on time.
 
Overall, this will be marked ‘yes’ if 11 of the 12 items (all except urine volume) are measured in first 4-hour period at the specified intervals (reviewer will determine for each item if occurred within the interval): fetal heart rate every 30 min, cervical
	
All labors with partograph or ePartogram
	
Same as above – except it will be for the first four hour period

	dilation every 4 hours, systolic and diastolic blood pressure every 4 hours, amniotic fluid if membranes rupture, moulding when present head descent every 2 hours, contractions every 30 min, pulse every 30 min, temperature every 2 hours, urine protein, acetone and volume, all at every 4 hours. ; and otherwise ‘no’. Binary variable.		
- Complete over entire labor for a subset of women who arrived at 4 or 5 cm			

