P2. Decision-making and actions taken to maintain normal labor (Tool 4)	Data on each partograph parameter will be entered for each time period, as well as actions taken in labor. Jhpiego clinical rules will be applied to the data in the extraction database to determine appropriate clinical actions for a labor without any complication. This is a binary variable.	Labors in which Section 3 marked as “Normal Labor”	First, we will examine the frequency/prevalence of each clinical action taken in normal labor and compare between the two study groups. Second, we will carry out same analysis as for Objective P1.
P3. Detection, decision-making and action to address deviations from normal labor and complications arising during labor—for ‘slow’ labor, prolonged labor, obstructed labor and cephalo-pelvic disproportion	Data on each partograph parameter will be entered for each time period, as well as actions taken in labor. Jhpiego clinical rules will be applied to the data in the extraction database to determine appropriate clinical actions for a labor with a specific complication. This is a binary variable.	Labors in which Section 3 marked “Slow labor, prolonged labor, obstructed labor or cephalo-pelvic disproportion”	First, we will examine the frequency/prevalence of each clinical action taken in selected complications and compare between the two study groups. Second, we will carry out same analysis as for Objective P1.
-- for all complications (Tool 4)	Same as above. A composite variable will be created for all complications. This is a binary variable.	Labors in which Section 3 marked as ANY complication	First, we will examine the frequency/prevalence of each clinical action taken in all

			complications and compare between the two study groups. Second, we will carry out same analysis as for Objective P1.
S1. Is facility use of ePartogram (vs. paper-partograph) associated with lower rate of...?			
From the Register Analysis			
Neonatal deaths <24 hours and (Tool 5)	Number of early neonatal deaths. This is a count variable.	All live births	We will compare means using t-tests across 2 groups. Next, we will use unadjusted regression models that account for clustering (correlation) of data within the facility. Poisson regression with offset term (or another appropriate model to be explored) will be used for bivariate and multivariable analysis.

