Intrapartum death (fresh stillbirth rate) (Tool 5)	Number of fresh stillbirths. This is a count variable.	All live births	Same as above.
Adverse perinatal events (Neonatal deaths <24 hours+ intrapartum death (fresh stillbirth rate))	Number of neonatal deaths and fresh stillbirths	All live births	Same as above.

Statistical analysis plan

Outcomes will be dichotomous, yes/no for each measure.

In the main statistical analysis of our primary outcomes, we will focus on program effect (intervention (ePartogram) group of facilities versus comparison (paper program) group of facilities) as the main predictor of interest. The analysis will be performed at the level of the individual case (partogram). In preliminary analyses we will conduct univariable and bivariable analyses to assess the distribution of key variables and joint distributions and unadjusted relationships.

In final analyses addressing study aims, we will fit multi-level, multivariable regressions models for the outcomes with adjustment for possible confounders and account for clustering by provider and/or study clinic by the use of GEE.

While we have selected clinics roughly matched between the intervention and comparison regions, we will still evaluate confounding to attain the least biased estimate of our intervention effect. Facility level possible confounders are: monthly case load of laboring women, number of providers, key equipment availability etc. Provider-level possible confounders that may be adjusted for are years of work experience since graduation and cadre. Woman-level possible confounders are age and parity.

5. Describe whether you are collecting or storing **personal identifiers**, and if yes, why you need them, and when and how you plan to dispose of them. Signatures on consent forms are considered to be identifiers.

Identifiers of Providers

Our study will assign each facility and each provider a study id number of the Health Worker Line Listing form to be updated monthly. This will be kept separately from partograph data.

partograph review analysis: the paper partograph has a place for a provider to sign it. When we scan/photocopy paper partographs, we will obscure the provider name (cover with lose paper) but will we add/write on it the provider study id number.

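### The primary analyses may be clustered by provider alone although facilities are assigned to arms, and no small-sample method is named for 12 facilities

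*Combined protocol and SAP*

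**What the plan says.** Section III.A (Phases) assigns facilities to the study groups purposively, within region. Section IV (Providers) adds: "All providers in a selected facility will be consented to the same study arm (ePartogram or paper partograph"). The sample size in III.B is inflated for facility clustering over 6 facilities per arm: "so we assume ICC of 0.15".

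The analysis in V.C.4 does not hold to that level. For P1, Table 5 states: "Bivariate analysis will be an unadjusted logistic regression accounting for clustering in the facility or in the provider". The P2 and P3 rows say: "Second, we will carry out same analysis as for Objective P1". The Statistical analysis plan calls the bivariable work preliminary, but its final models "account for clustering by provider and/or study clinic by the use of GEE". It also says: "The analysis will be performed at the level of the individual case (partogram"). Table 4 explains that provider IDs are put on the records "when names are obscured (to account for clustering of data in the provider").

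Only the regression models for S1 are tied to the facility. No small-sample correction, t reference or degrees of freedom is given for any outcome, and neither alpha nor power is stated.

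**The concern.** The arm is constant within a facility, so facilities are the independent units for the comparison. A model that treats providers as independent counts several providers from one hospital as separate evidence about the arm, and its standard error omits most of the variance between facilities. The wording permits this for all three primary questions, at both the unadjusted and the final step, and lets the level be chosen after the data are seen.

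There is a second gap. The usual sandwich variance is too small when there are few clusters, more so when they are very unequal in size or when facility-level covariates are added. The plan has 12 facilities, assumes a size coefficient of variation (COV) of 90%, and lists several facility-level confounders.

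The results are meant to inform the Ministry of Health on wider use. Chance differences between a dozen facilities could be reported as an ePartogram effect.

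**Working it through.** **The plan's own figure.** Alpha and power are unstated; two-sided 5% and 80% with the unpooled formula reproduce Table 1.
- Unadjusted n for 50% vs 80%: (1.96 + 0.8416)² × (0.25 + 0.16) / 0.30² = 35.8, stated as 36. The other two rows give 54.9 and 90.3, stated as 55 and 90.
- Labors per facility: 671 × 0.80 × 0.19 / 6 = 17.0.
- Design effect: 1 + (17.0 − 1)(1 + 0.90²)(0.15) = 5.34, stated as 5.3.
- 36 × 5.3 = 191 complicated labors; 191 / 0.19 ≈ 1004 partographs per arm.

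(The III.B text also prints 17.6 and 16.4 for cluster size and 0.80 for the COV. Table 1's values are used here.)

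**Inputs the plan does not give (assumed).** Providers per facility: 4, 8 or 16. The low end borrows from the interview sample ("assume 2 to 8 providers per site (average 4 providers")); the high end comes from the cap of 200 providers (200/12 = 16.7). Size COV is 0 or 0.9, extra within-provider correlation 0 or 0.10, and the true proportion 50%. ICC 0.15 is a P3 planning value applied to P1 as well; 0.05 and 0.01 show lower residual values.

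**Hand approximation for provider-only clustering.** True variance is inflated by DE_f = 1 + (m − 1)(1 + COV²)ρ. The model allows only DE_p = 1 + (m_p − 1)ρ, where m_p is labors per provider. The actual error rate is about 2[1 − Φ(1.96 √(DE_p/DE_f))]. With ρ = 0.15, COV 0.9 and 200 providers:
- P3: m = 191/6 = 31.8 and m_p = 1.91, so DE_f = 9.37, DE_p = 1.14, and the error rate is 2[1 − Φ(0.683)] = 49%.
- P1: m = 1004/6 = 167.3 and m_p = 10.04, so DE_f = 46.2, DE_p = 2.36, and the error rate is 2[1 − Φ(0.443)] = 66%.

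A favorable case for P3 (equal sizes, 4 providers per facility) gives DE_f = 5.63, DE_p = 2.04 and 24%.

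**Simulation under the null.** 6 vs 6 facilities, beta-binomial facility effects, logistic GEE with independence and exchangeable working correlation. Setting A splits labors evenly at random over providers (3000 runs per scenario). Setting B spreads up to 200 providers by facility volume at COV 0.9 (4000 runs per scenario). Rejection at nominal 5%, provider-only, unadjusted:

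| Facility ICC | P3, A | P3, B | P1, A | P1, B |
|---|---|---|---|---|
| 0.15 | 21–44% | 45–48% | 26–65% | 63–68% |
| 0.05 | 14–27% | 27–29% | 17–53% | 46–57% |
| 0.01 | 7–11% | 10–12% | 8–26% | 20–29% |

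With one to three facility-level covariates (A, P1 and P3 together), provider-only gives 23–64% at ICC 0.15, 14–51% at 0.05 and 8–27% at 0.01.

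P2 was not simulated. At 1004 × 0.81 = 813 labors per arm it should fall between P3 and P1.

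**Facility-level alternatives, same simulations.**
- Ordinary sandwich, normal reference: 8–17% (A) and 10–19% (B) unadjusted; 12–27% with one to three covariates. For P3 at ICC 0.01 this is mostly worse than provider-only.
- t-test on 12 facility proportions, 10 df: 4–6%.
- Regression of facility proportions on arm and one to three covariates: 4–6%. The two-stage version that also adjusts for provider and woman covariates: 4–7%.
- Mancl-DeRouen variance with t reference: 3–5.5% unadjusted, 2–5% with covariates.

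Monte Carlo standard error is at most 1.1 points.

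**The case against.** The strongest reply is that provider-only clustering is permitted, not planned. The final models are described as multi-level, the and/or wording allows both levels together, and the sample size and S1 both point to the facility. The plan also names no variance estimator, so every rate above depends on a default it never states, in a section that asks only for a brief plan.

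This is fair as far as it goes. If provider is nested in clinic, the first problem does not arise for the final models. But the text does not require nesting. Because providers sit inside facilities, a sandwich covering both levels is in effect the 12-facility sandwich, with the same small-sample problem. A random-effects model was not simulated.

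Other points that stand:
- The ranges are not bounds. They move with the provider distribution, as settings A and B show; the direction does not.
- If the balancing by region and volume succeeds, the unpaired t-test becomes conservative. In a check with equal-size facilities at ICC 0.15, it rejected about 3% when region explained half of the facility variance, and about 1.5% when pair matching did.
- An unadjusted difference in facility proportions cannot be compared directly with an adjusted labor-level odds ratio to judge confounding.
- The small-sample gap applies to S1 as well.
- A nominal 5% is only part of the uncertainty when assignment is purposive and two referral hospitals are fixed to intervention.

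**Conclusion.** The concern holds and must be fixed before analysis. An analyst who follows a permitted option as written gets a standard error that is far too small: about 21–48% false positives for P3 and 26–68% for P1 at the plan's ICC of 0.15, and still 7–12% and 8–29% at ICC 0.01. Provider-only clustering would be near 5% only if facility variance were almost zero, which contradicts the plan's own ICC. The facility level with default software settings gives 8–19% unadjusted, so naming the level alone does not solve it.

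The exact rates rest on assumed provider numbers, provider correlation and size distribution, on the inferred 5% level, and on facilities being exchangeable between arms. They describe sampling error only.

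**What to change.** In Table 5 and the Statistical analysis plan, replace the clustering phrases with: *Clustering is accounted for at the facility level; provider, if modelled, is nested within facility.* Then name one method per step before data are seen.
- **Unadjusted:** t-test on the 12 facility proportions, 10 df.
- **Adjusted, one of two.** (a) The planned GEE with a bias-corrected sandwich such as Mancl-DeRouen and a t reference on 10 df less one per facility-level covariate; this df rule is one convention and was conservative in simulation. (b) A two-stage analysis: adjust for woman and provider covariates without arm, then regress the 12 facility residuals on arm and facility covariates. This held about 5% with more power and keeps both steps at facility level.

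Amend the sentence on individual-case analysis to match the choice. List a few facility-level covariates in advance: each costs a degree of freedom, but omitting one risks residual confounding. Name a small-sample method for S1 too. State that these steps correct the standard error, not bias from purposive assignment. Do not rely on a permutation test until III.A (purposive) and V.C.6a (cluster-randomized) are reconciled.

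**Cost.** Wording and standard software, but less power. Going from a normal to a 10-df t reference takes nominal power from 80% to 71% (70%, 69% and 67% with one, two and three facility covariates) and widens intervals by 14–21%. Simulated power for 50% vs 80%, 191 labors per arm, COV 0.9, setting A:

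| | ICC 0.15 | ICC 0.05 |
|---|---|---|
| t-test, unadjusted | 65% | 90% |
| Mancl-DeRouen, unadjusted | 46–55% | 78–86% |
| Two-stage, 1 / 2 / 3 covariates | 58 / 56 / 53% | 84 / 84 / 77% |
| Mancl-DeRouen, 1 / 2 / 3 covariates | 37–44 / 32–35 / 24–26% | 67–73 / 61–66 / 46–48% |

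Covariates were simulated as unrelated to outcome; useful ones would win some power back. Setting B at ICC 0.15 gave 61% for the t-test and 41–53% for Mancl-DeRouen. There even the too-liberal ordinary facility sandwich reached only 73–76%, so not all of the gap to 80% is due to the fix. The t-test also weights facilities equally, so it estimates a difference in facility-average proportions rather than a labor-level odds ratio; the two differ if the effect varies with facility size.

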While study results demonstrated many benefits of ePartogram use, additional needed software refinements were identified, and further research is needed to assess its use in a greater variety of clinical settings. The proposed ePartogram effectiveness aims to further test the ePartogram software and use of ePartogram on clinical decision-making and care.

[figure not shown]
III. Study Design

- A. Provide an overview of your **study design and methods**.

Study Design

The study design is a quasi-experimental design evaluation with labor management outcomes compared for the study period between two study groups, intervention and control. The study will involve mixed methods – quantitative and qualitative data. The study is depicted below.

Figure 1. Study Design and Phases

Methods

The study will be conducted in the following phases.

Phases

- 1) An initial group of **facilities selected** for participation will be confirmed in Kisumu County and Meru County. A rapid formative assessment of possible facilities collected data on:
 - a. training needs on the paper partograph and
 - b. supplies, drugs and equipment available in stock for monitoring of normal labor, management of complications and referrals (facility assessment tool; this will be repeated every 3 months) (?).
 - c. percent of births recorded in the register at the facility in past 3 months that had a partograph started and used.
 - d. this activity received a non-HSR determination.
- 2) In each region, we expect approximately 6 facilities to participate. Within each region, equal numbers of facilities that will be purposively assigned to the study groups. Each study group will have facilities that have a similar birth volume, staffing levels, and BEmONC/CEmONC status, as much as possible so the two group are similar
 - a. Kisumu District Hospital and Meru Teaching and Referral Hospital must be intervention sites and will not be randomly allocated to the study group.
- 3) We will seek **approvals**:
 - a. 2 IRB approvals (JHSPH and KEMRI in Kenya) (see section X.E of this document).
 - b. Ministry of Health Approval to work in their sites
 - c. County Approvals (Kisumu and Meru)
 - d. Facility in-charge agreement will be sought at time of provider enrollment.
- 4) A similar three-day **whole-site training** will be carried out in each participating health facility in both study groups on labor management and partograph use by providers following Kenyan and WHO guidelines.

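### Arms are balanced within region, yet region is not a fixed model term and is misdescribed in the analysis plan; the facility covariate list is also open, with only 12 facilities

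*Combined protocol and SAP*

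**What the plan says.** **Allocation.** Section III.A (Phases, item 2) states "In each region, we expect approximately 6 facilities to participate" and "Within each region, equal numbers of facilities that will be purposively assigned to the study groups". With 12 facilities, that is about three per arm in each of Kisumu and Meru. The same item adds that "Kisumu District Hospital and Meru Teaching and Referral Hospital must be intervention sites".

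**Models.** For P1, Table 5 in Section V.C.4 specifies a clustered logistic regression with study group as the only predictor, then an adjusted model: "In multivariable analysis, other control factors added may be facility type, client volume, region or provider variables". P2 and P3 refer back to the P1 analysis.

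**Confounders.** The Statistical analysis plan under the same section says "While we have selected clinics roughly matched between the intervention and comparison regions, we will still evaluate confounding". It continues: "Facility level possible confounders are: monthly case load of laboring women, number of providers, key equipment availability etc". Region is not listed there.

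**Clustering.** The final models will "account for clustering by provider and/or study clinic by the use of GEE". No small-sample correction is mentioned.

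**The concern.** There are three linked weaknesses.

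1. Region is the one factor on which the arms are balanced by construction, so the analysis should condition on it. As written, it never enters the unadjusted models and may or may not enter the adjusted ones. If the counties differ, an analysis without region counts that difference as noise when it estimates the error of the arm effect.
2. The phrase about intervention and comparison regions describes a design in which arm and region coincide. An analyst who believed it would see region as inseparable from arm and leave it out.
3. Apart from region, Table 5 and the analysis plan name four distinct facility factors (type; volume or case load, which are nearly the same thing; number of providers; equipment) and then an etc. No rule says which will be used. With 12 facilities, fitting all four plus region leaves 12 − 1 − 1 − 1 − 4 = 5 degrees of freedom. Different choices can give materially different answers, and the adjusted model is the one that addresses the study aims.

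**Working it through.** **Step 1. The plan's own figure.** Table 1 (Section III.B) gives 36 unadjusted cases per arm for 50% vs 80%, a design effect of 5.3, and 1004 partographs per arm. Alpha and power are not stated; two-sided 0.05 and 80% reproduce the table.

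- n = (0.25 + 0.16) × 2.80² / 0.30² = 35.7
- cluster size = 536.8 × 0.19 / 6 = 17.0
- design effect = 1 + (17.0 − 1) × (1 + 0.90²) × 0.15 = 5.34
- 35.7 × 5.34 = 191 complicated labors; divided by 0.19, this is 1004 per arm

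The figure reproduces. It makes no allowance for region or for any covariate.

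**Step 2. Region in or out (P3).** The model takes one proportion per facility, with 12 facilities (two counties, three per arm in each) and a t test on residual degrees of freedom: 10 without region, 9 with it.

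- cases per facility = 191 / 6 = 31.8
- total between-facility variance = 0.15 × 0.25 = 0.0375
- binomial part = 0.205 / 31.8 = 0.0064, where 0.205 is the mean of 0.25 and 0.16
- a county difference d uses up d²/4 of the 0.0375, so within-county variance s² = 0.0375 − d²/4 + 0.0064
- true SE of the arm difference = √(s²/3), with or without region, because the arms are balanced
- without region, the expected residual variance is s² + 12 × (d/2)²/10, so the reported SE is too large when d > 0

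The values of d are assumptions. Power is simulated and good to about one point.

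| d (points) | s² | True SE | SE without region | Power without region | Power with region |
|---|---|---|---|---|---|
| 0 | 0.0439 | 0.121 | 0.121 | 61% | 60% |
| 10 | 0.0414 | 0.118 | 0.122 | 60% | 62% |
| 20 | 0.0339 | 0.106 | 0.124 | 60% | 71% |
| 30 | 0.0214 | 0.085 | 0.127 | 59% | 88% |

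The conservatism also shows under the null. In a separate simulation of the same layout, the test without region had true size of about 3.7%, 2.5% and 0.6% when region explained 10%, 25% and 50% of facility variance.

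The baseline is near 60% rather than 80% because 31.8 cases per facility replace the 17.0 in Table 1 and a t reference is used. That is a separate matter. The comparison between the last two columns is what counts here.

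**Step 3. Covariates under the planned type of analysis.** This is a simulated logistic GEE with independence working correlation, facility clusters, ICC 0.15, cluster-size CV 0.9 and 382 complicated labors (2 × 191), 3,000 runs per cell. Region is assumed to explain 25% of facility variance, and the added facility covariates are pure noise. The sandwich variance is uncorrected. Type I error at nominal 5%:

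| Model | z reference | t reference (12 − p df) |
|---|---|---|
| Arm only | 14% | 10% |
| + region | 20% | 15% |
| + region + 1 | 24% | 17% |
| + region + 2 | 28% | 20% |
| + region + 3 | 31% | 21% |
| + region + 4 | 34% | 24% |

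Rejection under the alternative (z reference) falls from 86% with region alone to 78% with region plus four. A t reference without a corrected variance is not enough. Adding region under an uncorrected sandwich itself raises type I error from 14% to 20%, so the region term and the variance correction have to come together.

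**The case against.** **Balance removes the problem.** If facilities are balanced within region, region cannot confound and may be left out. This stands in part: with equal facility counts the unweighted comparison is unbiased. But the reported error is still wrong if the counties differ. Moreover, the analysis is by case, and equal facility counts do not ensure equal case counts.

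**The size is unknown.** The documents give no county difference. At 10 points or less, region changes power by about two points at most. This stands, and the figures above are conditional. A reader might put the county gap on top of the ICC of 0.15 and find power without region of 51%, 40% and 28% at gaps of 20, 30 and 40 points. The documents do not support that: 0.15 was set for the whole heterogeneous set of sites, and the addition makes the total ICC 0.19, 0.24 and 0.31. A 40-point gap alone has variance 0.04, more than the entire 0.0375.

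**Extra covariates need not cost power.** This stands. With a facility-level t test, four noise covariates on top of region take power from about 82% to 53% (scaled to the plan's nominal 80%, region share 25%). But that is not the planned test, and prognostic covariates could gain power. Under the planned GEE the larger harm is false positives.

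**Facility adjustment is needed.** Assignment is purposive and two referral hospitals are fixed to the intervention arm, so the covariate list cannot be emptied on grounds of precision. This stands and shapes the fix.

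**Conclusion.** The concern holds in limited form. Three things rest on the text alone: region is the balancing stratum but not a fixed term; the analysis plan's description of regions contradicts Section III.A; and the facility covariate list is open and has no selection rule.

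The size rests on assumptions. Fixing region costs about 1 point of P3 power if the counties are alike and gains about 11 and 29 points at differences of 20 and 30 points, under a facility-level t test with total ICC 0.15. The rise in type I error from about 20% to 34% rests on an uncorrected sandwich, a 25% region share and uninformative covariates. No figures were derived for P1, P2 or S1.

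Two stronger readings are not supported. One is that omitting region and adding covariates must both lose power: the first depends on an unknown county difference, and the second on the test used and on how prognostic the covariates are. The other is that covariates will be chosen by their effect on the estimate: the plan says only that confounding will be evaluated. The defect is the missing rule.

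**What to change.** In Table 5 and the Statistical analysis plan:

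- Make region a fixed term in every P1 to P3 and S1 model, including those now called unadjusted.
- Correct the sentence on matching to say that facilities were matched between arms within each region.
- Delete the etc. and name one or two facility covariates in advance (for example case load and facility type), chosen on prior grounds because assignment is purposive. Put the other facility factors in sensitivity analyses, and fix the provider- and woman-level terms in advance too.
- Cluster at facility level, with a small-sample corrected variance and a t reference. Without this, the region term alone leaves type I error near 20%.

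The cost is a change of wording, with no new data. The downsides are about 1 point of power if the counties do not differ, and some residual facility imbalance that is examined only in sensitivity analyses.
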